6.7.3 Time schedule of ECG recordings and related PK blood sampling

The scheduled time points of ECG recordings and PK blood sampling are described in the CTP, section 10.6.

7 PLANNED ANALYSES

The labelling and display format of statistical parameters will follow BI standards (8).

Unless otherwise specified, outputs will be displayed separately for each part of the trial.

Descriptive statistics for continuous variables will generally contain number of patients in that patient set with non-missing values (N), Mean, Standard Deviation (SD), Minimum (Min), 25th percentile (Q1), Median, Q3 (75th percentile), Maximum (Max). In general, means, SDs, medians, Q1 and Q3 will be presented to one more decimal place than the raw data. Minima and maxima will be presented to the same number of decimal places as the raw data.

For time-to-event analysis tables, the set of statistics is: number of patients [N (%)], Number of patients with event [N (%)], Number of patients censored [N (%)], <Time to event> [months] followed by Q1 (25th percentile), Median, Q3 (75th percentile). If not specified otherwise, the duration as well as time to event will be displayed in months.

Tabulations of frequencies for categorical data will include all possible categories and will display the number of observations in a category as well as the percentage (%) relative to the respective treatment group total. Percentages will be rounded to one decimal place. In general a category "missing" will be displayed, if there are missing data for the corresponding variable. Percentages will also generally be based on all patients in the respective patient set whether they have non-missing values or not.

The primary analysis will include all treated (phase I escalation and expansion parts) or randomised patients (phase II part), following the ITT approach (as specified in Section 6.3).

Sort order for general categorical variables: If categories correspond to the collected categories on the eCRF and the table shells do not explicitly specify the ordering, the "default ordering" defined by the eCRF is to be used in such cases. If categories are derived the ordering as specified in the table shell document should be used; in general ordinal data (e.g. categorised continuous data) are to be displayed in ascending order.

The denominator of the main categories is defined by the number of patients in the used patient set. The main categories define the denominators of the subcategories. Subcategories should be indented and "[N (%)]" to be displayed only for the main category.

If a table includes only categorical data, "[N (%)]" is to be displayed in the column header.

In general, a "Total" column will be displayed in section 15.1 (trial subjects) of the CTR. In sections 15.2 and 15.3 of the CTR, a "Total" column will be displayed in phase I part outputs, but not in phase II outputs.

Abbreviations (e.g., Wors.) or acronyms (e.g., PD) should not be displayed in tables and patients data listings without any explanation. They will be either spelled out in the table or explained in footnotes (whatever is more reasonable from the programming point of view).

If applicable, conversion from days to weeks, months and years will be as follows:

- Weeks = days \div 7
- Months = days \times 12 \div 365.25

TSAP for BI Trial No.: 1280.8 Page 47 of 76

Proprietary confidential information © 2017 Boehringer Ingelheim International GmbH or one or more of its affiliated companies

• Years = days \div 365.25

In case a pooled analysis of 1280.4 and 1280.8 will be deemed appropriate, specifications of this analysis will be given in a separate CSAP before DBL.

7.1 DEMOGRAPHIC AND OTHER BASELINE CHARACTERISTICS

Only descriptive statistics are planned for this section of the report.

7.1.1 Disposition of patients

For patient disposition the standard descriptive table from the EOT/CSD (Company Standard Display) catalogue will be populated. Additionally, patients with discontinuations by initial treatment and the reasons will be listed and tabulated, overall and and for each treatment separately. The same output will also contain an overview of discontinued and non-discontinued, as well as completed and non-completed patients. In Appendix 16.1.9.2, a disposition table by country will be produced.

7.1.2 Important protocol violations

A table and a listing of patients with important protocol violations based on Table 6.2: 1 will be created in Section 15.1.3 and Appendices 16.2.3 and 16.1.9.2.3 (if needed) respectively, of the CTR.

7.1.3 Demographic and other baseline characteristics

Standard descriptive analysis and summary tables for all patients treated by initial treatment will be created for demographic data, oncological history and baseline conditions.

7.2 CONCOMITANT DISEASES AND MEDICATION

Only descriptive statistics are planned for this section of the report. Concomitant diseases will be coded similarly as adverse events based on the most current MedDRA version. Concomitant therapies (CT) will be coded according to World Health Organisation Drug Dictionary (WHO-DD). CT will be classified according to the Anatomical, Therapeutic, Chemical (ATC) classification system. The third ATC level will be used to categorise CTs by therapy type. In situations where a medical product may be used for more than one equally important indication, there are often several classification alternatives. As appropriate, patients receiving CTs with more than one possible ATC level-three category will be counted more than once; footnotes will clarify this possible double counting in tables.

Concomitant medications will be presented according to whether they are concomitant with the reception of study medication, or whether they were given prior to study medication. In case start and stop dates of the medications are completely missing, they are assigned as given prior to study medication.

7.3 TREATMENT COMPLIANCE

Compliance was not analysed separately by treatment received. The number of missed doses of any medication as recorded on the eCRF will be listed by patient.

7.4 PRIMARY ENDPOINTS

7.4.1 Phase Ib escalation

The primary endpoints are the MTD and the occurrence of DLT. The MTD is determined from the occurrences of DLTs during the MTD evaluation period (this period is defined in Section 5.1.1). An overall summary of the DLTs (see CTP Section 5.2.3 for definitions of DLT) which occurred during the MTD evaluation period and the on-treatment period will be provided for each dose cohort.

Patients that were treated but replaced for the MTD evaluation (see CTP Section 3.3.5) will be excluded from the MTD determination. Replacement of patients will be determined on a case by case basis; exclusion of these patients from the MTD evaluation will be confirmed by the trial team at the RPM prior to DBL.

A listing of patients with DLTs by initial treatment will be performed. A plot with an overview of the phase I escalation part (showing the patients and their assigned doses, replaced patients and patients with DLT) will be displayed.

At the end of the dose escalation phase, a safety analysis will be performed to determine the RP2D. The results will be documented for internal use and communication with the participating investigators (see also Section 9.1).

7.4.2 Phase Ib expansion cohort

Descriptive statistics for PSA response will be provided for all treated patients. Confirmed as well as unconfirmed responses will be displayed.

7.4.3 Phase II

The primary analysis for PFS based on investigator assessment will be conducted for all patients of the RS in the phase II part of this trial. PFS by investigator's assessment is the primary endpoint and will be assessed based on the Kaplan-Meier method for each treatment arm separately. Point estimates together with confidence intervals (based on Greenwood's method) will be provided for median PFS. An estimation of the effect on PFS of xentuzumab plus enzalutamide compared to the effect on PFS of enzalutamide will be given by the hazard ratio (HR) and its 95% confidence interval using a Cox proportional hazards model. The validity of the underlying assumptions of this model will also be checked. HR < 1 will favour treatment with xentuzumab plus enzalutamide; p-value from the two-sided log-rank test will be also displayed but it should be emphasised here that this is only to be understood in an exploratory way. The Breslow method for handling ties will be used. The censoring rules for PFS are as stated in Section 5.1.3.

TSAP for BI Trial No.: 1280.8

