Trial Protocol Version 12 Page 13 of 241

Proprietary confidential information. © 2022 Boehringer Ingelheim International GmbH or one or more of its affiliated companies. All rights reserved.

20. Tumour assessment: CT or MRI imaging of the chest, abdomen and pelvis at screening and prior to start C3D1 onwards (see below) according to modified RECIST criteria (version 1.1). If clinically indicated, imaging of any other known or suspected sites of disease using an appropriate method (CT scan or MRI) should be performed. After study entry, all lesions identified during the screening should be followed up at all specified imaging time points. The same radiographic procedure must be used throughout the study. See section 5.1.2.1

A bone scan should be performed at screening, prior to the start C3D1and onwards according to schedule below.

Tumour assessment and bone scans will be performed at the following time points until progression/start of further anti-cancer therapy (assessments may be performed up to 7 days prior to the scheduled assessment date):

- At screening: all patients will have a CT or MRI and bone scan at screening, unless valid results are available from a scan performed within 28 days prior to start of study treatment, as part of routine clinical practice
- Week 8 (49-56 days after randomisation)
- Week 16 (105-112 days after randomisation)
- Week 24 (161-168 days after randomisation)
- Every 12 weeks thereafter (i.e., during week 35-36 (245-252 days after randomisation), during week 47-48 (329-336 days after randomisation), etc...)

In the event of an interruption/delay to treatment the tumour assessment schedule should not be changed.

- 21. All patients should have a tumour assessment/bone scan at EOT visit regardless of the reason for discontinuation, unless the last evaluation was performed within 4 weeks of EOT.
- 22. Optional physical examination.
- 23. If not recovered at EOT, or new AE, or drug related death.
- 24. Dispensing of enzalutamide at every weekly visit. However for patients in Arm B and those patients in Arm A which discontinue BI 836845 permanently, from cycle 4 onwards, enzalutamide will be dispensed only on Day 1 of each cycle, e.g. C4D1, C5D1 onwards.
- 25. For more details on patient completion, see section 6.1.3.5

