7.3.1 Primary analyses

The primary analysis of PFS for the phase II will be conducted and reported when approximately 60 patients (out of 80 randomised patients) have progressed or died. However, it may be performed with fewer events after approximately 23 months of the first patient being randomized in the Phase II part. Any additional information collected after the data cut-off for the primary analysis will be part of a revised report.

A Cox proportional hazards model (using Breslow's method for dealing with ties) will be used to analyse PFS for the phase II patients. The model will be used to estimate the hazard ratio of BI 836845 in combination with enzalutamide vs. enzalutamide alone, where a value

Doc. No.: c02304008-15

06 Jun 2022

Page 97 of 241

Trial Protocol Version 12 Proprietary confidential information. © 2022 Boehringer Ingelheim International GmbH or one or more of its affiliated companies. All rights reserved.

of less than one favours BI 836845 in combination with enzalutamide. The estimate of the hazard ratio, its asymptotic two-sided 95% confidence interval and asymptotic two-sided pvalue when testing against a value of one will be displayed. The proportional hazards assumption will also be checked.

The Kaplan-Meier survival rate quartiles (with two-sided 95% confidence intervals found using Greenwood's variance estimate) will be presented for each treatment group. The equality of the survival curves will be tested by the log-rank test at the 5% significance level.

PFS for phase Ib expansion, patients will be summarized separately to phase II patients using descriptive statistics only.

PFS is defined as the time from randomisation for phase II (from the start of treatment for phase Ib) to disease progression in bone based on prostate cancer clinical trials working group (PCWG2) criteria, or soft tissue based on modified RECIST 1.1 (as detailed in Section 5.1.2.1), or death. Patients without image-based progression or death at any time during the study will be censored at the date of their last imaging. Detailed censoring rules will be specified in the TSAP.

For the exploratory expansion cohort, PSA response, defined as a decline in PSA >50% (which is confirmed by a second value 3 to 4 weeks apart), will be used as primary endpoint. Descriptive statistics for PSA response will be provided for all treated patients.

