5.1.3 Phase II

The primary endpoint for the phase II part of the study is PFS based on investigator assessment.

PFS is defined as the time from randomisation until radiological tumour progression in bone (based on PCWG2 criteria) or soft tissue (based on modified RECIST 1.1) or death from any cause, whichever occurs earlier.

Tumour assessments will be performed at screening, week 8, week 16, week 24 and then every 12 weeks thereafter (more details in CTP Flow Chart).

For each follow-up (FU) imaging time-point an overall tumour response will be determined for soft tissue according to modified RECIST 1.1 (R09-0262 and Appendix 10.4 of the CTP) and for bone according to the prostate cancer clinical trials working group (PCWG2) criteria (R13-1642). The overall tumour response for each imaging time-point according to modified RECIST 1.1 will be selected from the following categories: Complete Response (CR); Partial Response (PR); Stable Disease (SD); No disease (ND); Progressive Disease (PD); Non-CR/Non-PD; Not Evaluable (NE). The overall tumour response for each imaging time-point (if clinically indicated) for bone lesion will be selected from the following categories: Non-progressive disease (Non-PD); Progressive disease (PD); Not Evaluable (NE).

Some patients enter the trial without any target or non-target lesion according to RECIST 1.1. Until new lesions appear and a progression is reported for this patient, the response assessment for such patients will be set to No Disease (ND) (see also Section 5.4.7).

For details on the imaging process and RECIST evaluation, see Section 5.1.2 and Section 10.4 of the CTP.

Derivation of endpoint PFS

Derivations below are described in days. However, the endpoints below will be presented in months in the outputs produced for the Clinical Trial Report (CTR).

For patients with 'event' as an outcome for PFS: (according to modified RECIST version 1.1 or PCWG2)

• PFS [days] = date of outcome - date of randomisation + 1.

For patients with 'censored' as an outcome for PFS: (according to modified RECIST version 1.1 or PCWG2)

• PFS (censored) [days] = date of outcome - date of randomisation + 1.

The censoring rules for PFS (i.e. outcome and date of outcome) are given in Table 5.1.3: 1. Clinical disease progression will not be considered for determination of a PFS event, unless the outcome of the progression is death.

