Alive and not progressed, two or more consecutively missed radiological assessments	Censored	Date of last radiological assessment prior to missed radiological assessments
Progressed, zero or one missed radiological assessment prior to progression	Event	Date of radiological assessment of progression
Progressed, but two or more consecutively missed radiological assessments prior to progression	Censored	Date of last radiological assessment prior to missed assessment
Death but no progression, zero or one missed radiological assessment prior to death	Event	Date of death

Table 5.1.3: 1 Derivation rules for PFS (cont.)

Situation	Outcome (event or censored)	Date of outcome		
Death without progression, but two or more consecutively missed radiological assessments prior to death	Censored	Date of last radiological assessment prior to missed assessments		
Initiation of subsequent anti-cancer therapy				
Subsequent anti-cancer therapy started before progression or death	Censored	Date of last radiological assessment before subsequent anti-cancer therapy		
No baseline and post- baseline imaging and subsequent-anti cancer therapy started prior to a death	Censored	Date of randomisation (or first treatment administration, in non-randomised trials)		

Data will be carefully checked in order to detect missing assessments. In case further rules are needed, these will be discussed at a BRPM and added in a revision of the TSAP.

In order to identify that consecutive imaging time-points are missing for a given patient, a nominal time point [8, 16, 24, and then every 12 weeks thereafter] will be assigned to the assessments. This is achieved by creating windows for every assessment. The windows are defined in Table 6.7.2: 1.

Last evaluable imaging

An evaluable radiological image for the censoring of PFS is an image for which an overall response assessment of SD, Non-PD, Non-CR/Non-PD, PR or CR has been assigned. This is used for censoring of patients without progression at end of trial, or censoring prior to missed assessments or censoring prior to subsequent anti-cancer therapy. If the bone and the soft tissue assessment have been done at different dates, the date of the first assessment will be the date of censoring.

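### Breslow tie handling in the primary Cox model pulls the PFS hazard ratio slightly towards 1; Efron is a cheap improvement with a small expected effect

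*SAP*

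**What the plan says.** The two documents agree on the method. SAP 7.4.3 states: "The Breslow method for handling ties will be used". Protocol 7.3.1 specifies the Cox model "using Breslow's method for dealing with ties". The text available gives no reason for the choice and plans no other tie method as a check.

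Four other provisions determine how many ties there will be:

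- **Time scale.** SAP 5.1.3 counts in days: "PFS [days] = date of outcome - date of randomisation + 1".
- **Event date.** A progression takes the "Date of radiological assessment of progression" (SAP Table 5.1.3: 1). A death that counts as an event takes the date of death. The nominal windows in SAP 6.7.2 serve only to identify missed scans.
- **Schedule.** Phase II scans are due at weeks 8, 16 and 24 from randomisation and every 12 weeks after that (Protocol, phase II flow chart, footnote 20). The footnote adds that "assessments may be performed up to 7 days prior to the scheduled assessment date", so the week 8 scan may fall on any of days 49 to 56.
- **Timing of the analysis.** It is planned when "approximately 60 patients (out of 80 randomised patients) have progressed or died", but "it may be performed with fewer events after approximately 23 months of the first patient being randomized" (Protocol 7.3.1).

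Protocol 7.2 bases inference on the size of the observed effect, not on a formal test. Protocol 7.6 sizes the trial on the chance of observing a small hazard ratio. SAP 7.5.2.3 and Protocol 7.3.2 carry the primary Cox method over to PFS by central review, OS and time to PSA progression.

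**The concern.** Breslow's approximation is biased towards no effect when many events share a time. This design produces shared times: every patient is scanned in the same few windows, and the planned medians of 3 and 4.3 to 4.6 months (Protocol 7.6) put most progressions at the first three scans. The trial is to be read on the size of the observed hazard ratio, so a shift in the point estimate is a shift in the quantity that readers will use. Efron's approximation is generally closer to the continuous-time fit and is available as an option in the same software procedure. The open question is how large the shift is under the schedule as written.

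**Working it through.** **1. The plan's own figures.** The footnote to Table 7.6: 2 gives P(observed HR ≤ X) = Φ[(ln X − ln HR)/√(4/d)]. With d = 60, √(4/60) = 0.258. At X = 0.8:

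- HR 0.65: Φ(0.2076/0.258) = 0.789 (table 0.79)
- HR 0.70: Φ(0.1335/0.258) = 0.698 (table 0.70)
- HR 1.0: Φ(−0.2231/0.258) = 0.194 (table 0.19)

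All 16 rows reproduce to within 0.005. The formula takes no account of ties.

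**2. Expected ties, by hand.** Use the protocol's rates of 0.231 and 0.151 per month and 40 patients per arm. Eight weeks is 56 × 12/365.25 = 1.84 months. The expected number of events first seen at week 8 is 40(1 − e^(−0.425)) + 40(1 − e^(−0.278)) = 13.8 + 9.7 = 23.5. The same calculation gives 16.4 at week 16 and 11.5 at week 24. Reducing these by 15% for permanently censored patients gives about 20, 14 and 10, or 44 of the 60 events. Spread over 8 days, that is about 2.5, 1.7 and 1.2 events per day: many ties, but small ones. All on one day, the first tie would be about 20.

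**3. The two methods.** For d events tied at one time, with risk-set sum S and tied-event sum D (each a sum of e^(βz)), Breslow uses the denominator S^d. Efron uses the product over l = 0, …, d − 1 of (S − (l/d)D). Breslow therefore keeps all tied patients in the risk set throughout. With ties of 5 that matters little; with ties of 20 it matters more.

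**4. Simulation.** There were 6000 trials per scenario, with 40 + 40 patients and exponential PFS with medians 3 and 4.6 months (HR 0.652). Progression was dated at the next scan, 15% of patients were permanently censored, and the cut-off was 60 events or 23 months. Both tie methods were fitted to the same data, and a third fit used the true continuous times. Three inputs are assumptions because the documents do not give them: accrual of 10.5 months (midpoint of the 9 and 12 in Table 7.6: 3), 10% of events being deaths on exact days (range 0 to 25%), and the spread of scan days within the window.

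| Scan days | Events tied | Largest tie | Geometric mean HR, Breslow | Efron | Continuous | P(HR ≤ 0.8), Breslow | Efron |
|---|---|---|---|---|---|---|---|
| Even over 8 days | 66% | 4.8 | 0.650 | 0.644 | 0.641 | 0.786 | 0.790 |
| Last 3 days only | 84% | 8.5 | 0.659 | 0.644 | 0.641 | 0.776 | 0.790 |
| Half on the due day | 70% | 10.9 | 0.661 | 0.645 | 0.642 | 0.767 | 0.785 |
| All on one day | 89% | 18.8 | 0.683 | 0.645 | 0.642 | 0.756 | 0.795 |

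The shifts are 0.006, 0.015, 0.016 and 0.038 in the hazard ratio. With scans spread evenly, the share of tied events runs from 54% (25% deaths) to 75% (no deaths). With all scans on one day and no deaths, 99% of events are tied and the ratio of the two estimates is 1.073. In single trials, Breslow was the estimate nearer 1 in about 87 to 96% of runs.

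**5. Size against the noise.** With scans spread evenly, mean log HR is −0.4308 (Breslow) and −0.4394 (Efron). The gap of 0.0086 is 2% of the log HR and about 3% of its standard error (0.267). With all scans on one day the gap is 0.4391 − 0.3808 = 0.058, about 0.22 of a standard error.

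**6. No effect (HR 1.0; planned P(HR ≤ 0.8) = 0.19).** Breslow to Efron: 0.191 to 0.197 (even), 0.186 to 0.199 (half on the due day), 0.154 to 0.196 (one day). The SD of the log HR at HR 0.652 goes from 0.264 to 0.270 (even) and from 0.231 to 0.266 (one day).

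**7. Time to PSA progression.** PSA is drawn on day 1 of each cycle from cycle 3, with a ±1 day allowance in the flow chart. For patients whose PSA never declines, only values from day 84 count (SAP 5.2.2.3). The windows are therefore narrower than for scans. A rough simulation (800 trials per setting) borrowed the PFS medians. It varied the share of early progressors without a decline from 0 to 100%, and the share randomised 1 to 3 days early from 0 to 30%. Breslow's hazard ratio was 0.008 to 0.014 nearer 1 than Efron's.

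**The case against.** The strongest reply is that nothing here is wrong. Breslow is a standard method, both documents name it, and under the documented window it delivers the planned probabilities: 0.786 against 0.79, and 0.191 against 0.19. That stands, and it is why this is an improvement and not a correction.

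A reader might infer that PFS can change only on scan days, so that almost every event is tied. The SAP does not support this. Deaths are events on their own dates, progression is dated at the actual scan, and with several imaging dates the earliest date is used for progression. End-of-treatment scans also fall off schedule, and the simulation does not model them. All of this spreads event times, so the one-day row is an extreme and not an expectation. Equally, the documents do not exclude clustering.

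A second reply is that with evenly spread scans Breslow (0.650) lies nearer the true 0.652 than Efron (0.644). As arithmetic this is correct. But the continuous-time Cox fit itself averages about 0.641 in these simulated trials, so Breslow's advantage is two small biases offsetting each other. It is gone once scans cluster: on one day Breslow is 0.031 from the true value and Efron 0.007.

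A reader might also infer that a decision rule at 0.8 is being missed. No such rule is stated. Protocol 7.2 refers to PFS and other efficacy endpoints including OS, and Table 7.6: 2 lists 0.7, 0.8, 0.9 and 1.0.

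Last, Efron is not free of cost: the estimate varies slightly more, and Efron is itself an approximation. Both points stand.

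**Conclusion.** The point holds as a low-priority improvement. Breslow is specified where tied event days are common, and it moves the PFS hazard ratio towards 1 by about 0.006 (1%) if scans use the whole window. The movement is about 0.015 with partial clustering and about 0.04 (6%, or 7% with no deaths) if all scans fall on one day. The chance of observing 0.8 or less falls by under 1 point, 1 to 2 points and about 4 points respectively. Efron comes within 0.004 of the continuous-time fit in these scenarios, so it nearly removes the shift.

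The sizes rest on assumed scan-day spread, death share and accrual length; the direction does not. The sizing in Protocol 7.6 is not in error. The argument does not extend to OS, because deaths fall on exact days and are not tied by the scan schedule.

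**What to change.** **In a plan not yet analysed:** replace Breslow with Efron in SAP 7.4.3 and Protocol 7.3.1 for the Cox models of PFS (investigator and central review) and time to PSA progression. OS is little affected and may follow for consistency.

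**In this trial:** the revised SAP is dated 28 September 2017, and global amendment 7 of 6 February 2018 (Protocol section 11) already refers to the phase II results. Replacing the primary method now would be post hoc. Keep Breslow as the prespecified analysis and report Efron beside it, labelled as a sensitivity analysis. Also state the number of distinct event days and the largest tie, so that a reader can see which row of the table applies.

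**Cost:** one software option and a sentence in each document, with no added patients or data. The SD of the log HR rises slightly (about 0.264 to 0.270 with evenly spread scans), and the chance of a ratio of 0.8 or less under no effect stays at about 0.20, close to the planned 0.19.
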